11.4.3 Handling of missing values/censoring/discontinuations

Missing values will be assumed missing at random. No imputation of missing values will be done for any analyses.

11.5 Analysis of secondary and exploratory variables

The number and percentage of subjects using loperamide will be tabulated by treatment. Total weekly loperamide use (in mg) will be summarized by treatment and visit (including baseline). The stool index, calculated as [weekly stool frequency*mean stool form]+loperamide use [weekly mg*3], will also be summarized and analyzed using a linear mixed effects model including sequence, period and treatment as fixed effects and subject nested within sequence as a random effect.

Corporate Confidential Information

11.5.2 Safety

Vital signs

All vital signs data will be listed by treatment sequence, patient, and visit/time and if ranges are available abnormalities (and relevant orthostatic changes) will be flagged. Summary statistics will be provided by treatment and visit/time.

ECG evaluations

All ECG data will be listed by treatment sequence, patient and visit/time, abnormalities will be flagged. Summary statistics will be provided by treatment and visit/time.

Clinical laboratory evaluations

All laboratory data will be listed by treatment sequence, patient, and visit/time and if normal ranges are available abnormalities will be flagged. Summary statistics will be provided by treatment and visit/time. Baselines will be the last available measurement in each treatment period post washout and prior to dosing.

Adverse events

All information obtained on adverse events will be displayed by treatment and patient.

The number and percentage of patients with adverse events will be tabulated by body system and preferred term with a breakdown by treatment. An adverse event starting in one period and continuing into the next period is counted only in the onset period. A patient with multiple adverse events within a body system and treatment period is only counted once towards the total of this body system and treatment.

11.5.3 Pharmacokinetics

For standard pharmacokinetic abbreviations and definitions see the list provided at the beginning of this protocol.

All patients with at least one period of evaluable pharmacokinetic (PK) parameter data will be included in the pharmacokinetic data analysis.

The following pharmacokinetic parameters and other appropriate parameters may be determined for LJN452:

AUClast, AUCtau, Cmax, Cmin, Cav,ss, Tmax, CL/F, Racc (accumulation ratio = AUCtau,ss/AUCtau,day 1) may be assessed from plasma concentration-time data.

Corporate Confidential Information

non-compartmental method(s) with Pheonix (Version 6.3 or higher).

11.5.4 Pharmacokinetic / pharmacodynamic interactions

The relationship between PK and key PD parameters (for example, change in stool frequency) may be explored, if needed.

11.5.5 Other assessments

Corporate Confidential Information

11.6 Sample size calculation

Corporate Confidential Information

11.7 Power for analysis of key secondary variables

No assessment of power for the secondary objectives has been done.

11.8 Interim analyses

Corporate Confidential Information

12 Ethical considerations

12.1 Regulatory and ethical compliance

This clinical study was designed and shall be implemented and reported in accordance with the ICH Harmonized Tripartite Guidelines for Good Clinical Practice, with applicable local regulations (including European Directive 2001/20/EC, US Code of Federal Regulations Title 21, and Japanese Ministry of Health, Labor, and Welfare), and with the ethical principles laid down in the Declaration of Helsinki.

12.2 Responsibilities of the investigator and IRB/IEC

Before initiating a trial, the investigator/institution should obtain approval/favorable opinion from the Institutional Review Board/Independent Ethics Committee (IRB/IEC) for the trial protocol, written informed consent form, consent form updates, patient recruitment procedures (e.g. advertisements) and any other written information to be provided to patients. Prior to study start, the investigator is required to sign a protocol signature page confirming his/her agreement to conduct the study in accordance with these documents and all of the instructions and procedures found in this protocol and to give access to all relevant data and records to Novartis monitors, auditors, Novartis Quality Assurance representatives, designated agents of Novartis, IRBs/IECs, and regulatory authorities as required. If an inspection of the clinical site is requested by a regulatory authority, the investigator must inform Novartis immediately that this request has been made.

For multi-center trials, a Coordinating Investigator will be selected by Novartis around the time of Last Patient Last Visit to be a reviewer and signatory for the clinical study report.

12.3 Publication of study protocol and results

Novartis assures that the key design elements of this protocol will be posted in a publicly accessible database such as clinicaltrials.gov. In addition, upon study completion and finalization of the study report the results of this trial will be either submitted for publication and/or posted in a publicly accessible database of clinical trial results.

13 Protocol adherence

This protocol defines the study objectives, the study procedures and the data to be collected on study participants. Additional assessments required to ensure safety of patients should be administered as deemed necessary on a case by case basis. Under no circumstances should an investigator collect additional data or conduct any additional procedures for any research related purpose involving any investigational drugs.

Investigators must apply due diligence to avoid protocol deviations. If the investigator feels a protocol deviation would improve the conduct of the study this must be considered a protocol amendment, and unless such an amendment is agreed upon by Novartis and approved by the IRB/IEC/REB it cannot be implemented. All significant protocol deviations will be recorded and reported in the CSR.

1.1 Scope of document

The RAP documents contain detailed information to aid the production of Statistics & Programming input into the Clinical Study Report (CSR) for trial CLJN452X2202.

The Statistical analysis plan (SAP) describes the implementation of the statistical analysis planned in the protocol.

1.2 Study reference documentation

This SAP has been developed using Clinical Trial Protocol version v02 (incorporating Amendment 2) approved by the SRC on 09 August 2016.

1.3 Study objectives

1.3.1 Primary objectives

- To determine the safety and tolerability of LJN452 in patients with primary bile acid diarrhea (pBAD)
- To assess the effect of LJN452 on clinical symptoms experienced by patients with pBAD

1.3.2 Secondary objectives

- To assess the pharmacokinetics of LJN452 in pBAD patients
- To assess the effect of LJN452 on use of rescue medications during the study period

[figure not shown]
Corporate Confidential Information

1.4 Study design and treatment

This is a multi-center, double blind (patient and investigator blind, sponsor open label), randomized placebo controlled, crossover study to assess safety, tolerability and efficacy of LJN452 in patients with pBAD. In this study approximately 30 patients will be enrolled to have 24 completers.

This is a non-confirmatory trial.

Figure 1-1 Study design

In treatment period 1 on Day 1 patients will receive either 60 µg LJN452 or placebo orally once daily for 14 days in a 1:1 ratio. Pharmacokinetic (PK), pharmacodynamic (PD) and safety samples will be collected on Day 1 for up to 8 hours post dose and on Day 2 pre-dose, which corresponds to 24 h after Day 1 dosing.

Patients will be handed over trial medication, to be administered at home enough to cover dosing for 14 days in each period. Throughout the 14 days of the treatment period, patients will be directed to take study drug at home with water in the morning in a fasting state, 2 hours prior to the first meal of the day, preferably at the same time of the day.

After 2 weeks of treatment with LJN452 or placebo, patients will undergo a washout of at least 7 days, up to a maximum of 28 days. At the end of the washout period, patients will return to the study site for period 2 of the study. Period 2 will be identical to period 1 except that the treatments will be crossed over.

The randomization will be maintained at a 1:1 ratio over the entire study in order to avoid any sequence bias.

2 First interpretable results (FIR)

First interpretable results (FIR) will be provided for this trial.

The study FIR template (mock slides) can be found in CREDI in the study RAP folder.

The template shows the analysis / results to be presented in the FIR. Study outputs required to be created at the time of the FIR will be highlighted in TFL shells document and marked as "Key" in the Programming Deliverables Tracker (PDT) output list.

3 Interim analyses

Corporate Confidential Information

4 Statistical methods: Analysis sets

For patients for which the actual treatment received does not match the randomized treatment the treatment actually received will be used for the analysis.

For patients for which the actual sequence of treatments received does not match the randomized sequence of treatments, the actual sequence will be used for analysis involving a sequence component (e.g. ANOVAs with a sequence effect) if the actual sequence is one of the sequences planned in the study design. If the actual sequence is not one of the sequences planned in the study design, the randomized sequence will be used for analysis involving a sequence component but data points from periods in which the patient has not received the randomized treatment will be excluded from the analysis.

The safety analysis set will include all patients that received any study drug.

The PK analysis set will include all patients with available PK data and no protocol deviations with relevant impact on PK data.

The PD analysis set will include all patients with available PD data and no protocol deviations with relevant impact on PD data.

The analysis sets and protocol deviation codes are related as follows:

Table 4-1 Protocol deviation codes and analysis sets

Category Deviation code	Text description of deviation	Data exclusion
Patients are excluded from all (safety) analysis in case of these PDs:		Exclude patient completely from all analysis sets
I01	ICF not obtained	Yes
S01	Subject did not receive any study drug	Yes

Category Deviation code	Text description of deviation	Data exclusion
Patients are excluded from PK analysis in case of these PDs:		
S01	Subject did not receive any study drug	Yes
I01	ICF not obtained	Yes
Patients are excluded from PD analysis in case of these PDs:		
S01	Subject did not receive any study drug	Yes
I01	ICF not obtained	Yes
Patients are excluded from PK and PD analysis in case of these PDs:		
S01	Subject did not receive any study drug	Yes
I01	ICF not obtained	Yes

If updates to this table are needed, an amendment to the SAP needs to be implemented prior to DBL.

5 Statistical methods for Pharmacokinetic (PK) parameters

5.1 Variables

The following and other appropriate pharmacokinetic parameters may be determined using the actual recorded sampling times and non-compartmental method(s) with Phoenix WinNonlin (Version 6.3 or higher): AUClast, AUCltau, Cmax, Cmin, Cav,ss, Tmax, CL/F, Racc (accumulation ratio = AUCltau,ss/AUCltau,day 1).

5.2 Descriptive analyses

LJN452 concentration data will be listed by patient and visit/sampling time point. Descriptive summary statistics will be provided by visit/sampling time point.

Pharmacokinetic parameters will be calculated as described in Section 5.1 of the protocol and will be listed by patient and visit. Summary statistics will include mean (arithmetic and geometric), SD, CV (arithmetic and geometric), median, minimum and maximum. An exception to this is Tmax where median, minimum and maximum will be presented. Concentrations below LLOQ will be treated as zero in summary statistics and for PK parameter calculations. A geometric mean will not be reported if the dataset includes zero values.

5.2.1 Graphical presentation of results

Arithmetic mean (SD) and geometric mean (95% CI) plasma concentration data will be plotted across time.

Overlaying individual plasma concentration-time profiles will be generated.

Individual plasma concentration-time profiles will be generated.

Corporate Confidential Information

6 Statistical methods for Pharmacodynamic (PD) parameters

6.1 Primary objective

To assess the effect of LJN452 on clinical symptoms experienced by patients with pBAD.

6.1.1 Variables

The primary analysis variables are: a) stool frequency, b) and stool form assessed by the Bristol stool chart.

6.1.2 Descriptive analyses

Summary statistics (including median and IQR) of the stool frequency and average stool form (weekly and biweekly) for each treatment as well as the difference and % change between the 2 treatments will be provided by visit. Baseline data will be summarized by treatment and visit. The number and percentage of patients with each stool form will be provided by treatment and visit. The stool frequency and stool form data will be listed by treatment sequence, patient and visit.

6.1.3 Statistical model, assumptions and hypotheses

A repeated measures analysis will be done for the two-dimensional endpoint: weekly stool frequency and the corresponding average stool form. The analysis will include fixed effects for sequence (Drug/Placebo or Placebo/Drug), Treatment (Week 1 drug, Week 2 drug, Week 1 placebo or Week 2 Placebo), and period (1 or 2). The model will assume an arbitrary 2 by 2 covariance matrix for the two-dimensional endpoint (frequency, form) and a compound symmetry covariance matrix for each individual end point. Point estimates of the weekly & biweekly treatment effect on stool frequency and the corresponding average stool form will be reported together with 95% simultaneous confidence intervals (confidence ellipsoids).

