2.1 Primary objective(s)

Primary objective(s)	Endpoints related to primary objective(s)

• To determine the safety and tolerability of LJN452 in patients with primary bile acid diarrhea.• To assess the effect of LJN452 on clinical symptoms experienced by patients with primary bile acid diarrhea.	
• Safety endpoints include type and frequency of adverse events, serious adverse events, and laboratory, vital signs, physical, and ECG abnormalities.• Changes from baseline in stool frequency and in stool form per Bristol Stool Chart.

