3.1 Study design

This is a multi-center, double blind (patient and investigator blind, sponsor open label), randomized placebo controlled, crossover study to assess safety, tolerability and efficacy of LJN452 in patients with primary bile acid diarrhea (pBAD). In this study approximately 30 patients will be enrolled to have 24 completers.

This is a non-confirmatory trial.

Each patient will undergo a screening period (28 days), run-in period (washing out previous treatment effect) (up to 14 days), 2 treatment periods (14 days each), washout period (at least 7 up to 28 days) between the treatment periods and end of study.

Figure 3-1 Study design schematic

Patients will be assessed for eligibility to enter the study at the screening visit.

Each patient will perform following visits

Screening visit: Day -28 to -2

During the screening period all patients will undergo screening assessment, which may be completed over multiple visits as per the patient's convenience. The screening results will be valid for 28 days, if any patient is beyond the screening validity, the patient can be re-screened. Results for all screening assessment must be available before the baseline/Day 1 pre-dose assessment.

If the eligibility is confirmed patients will be asked to discontinue their sequestrants. Patients will be handed over patient diary to record their daily stool type and frequency using Bristol Stool Chart and use of rescue medication (loperamide intake). The patient diary is expected to be used by patients' throughout the study duration.

Rescue medication will be loperamide only and patients will be instructed to take 2 mg dose only after passage of 4 stools of Bristol Stool Scale Type 6 (Fluffy pieces with ragged edges, a mushy stool) or Type 7 (Watery, no solid pieces, entirely liquid). This dose may be repeated only after 4 hours have elapsed or passage of 4 further stools of Type 6 or 7 (whichever occurs first). A total of no more than 16mg of loperamide may be taken in a 24 hour period. No BA sequestrants should be used by the patients during this study.

Run-in period (Day -7 to -1 or Day -14 to -1)

Patients who have not used bile acid sequestrants for pBAD in the previous week at the time of screening will be evaluated for inclusion/exclusion criteria during the screening visit, and if found eligible will enter a 1 week run in period (Day -7 to -1) prior to the double blind randomized treatment phase.

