6.1.3.3 Supportive analysis

Baseline weekly stool frequency and the corresponding average stool form will be analyzed using the same method as described in Section 6.1.3 to assess unequal carryover effects.

The number and percentage of subjects using loperamide will be tabulated by treatment. Total weekly loperamide use (in mg) will be summarized by treatment and visit (including baseline). The stool index, calculated as [weekly stool frequency*mean stool form]+loperamide use [weekly mg*3], will also be summarized and analyzed using a linear mixed effects model including sequence, period and treatment as fixed effects and subject nested within sequence as a random effect.

Corporate Confidential Information

7 Statistical methods for safety and tolerability data

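### The primary stool model uses no baseline term although period-specific baselines are collected and modelled elsewhere, so the drug-placebo estimate may be less precise than the data allow

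*SAP*

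**What the plan says.** SAP 6.1.3 describes the primary efficacy analysis: "A repeated measures analysis will be done for the two-dimensional endpoint: weekly stool frequency and the corresponding average stool form". Its mean structure is given as: "The analysis will include fixed effects for sequence (Drug/Placebo or Placebo/Drug), Treatment", the last with four levels (drug or placebo, by week), plus period. The covariance is unstructured between the two endpoints, with "a compound symmetry covariance matrix for each individual end point". Protocol 11.4.2 has the same model. The response is the weekly value itself, and neither document puts a baseline in this model.

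The baseline data exist. Protocol 3.1 says: "The patient diary is expected to be used by patients' throughout the study duration". It sets a run-in of 7 or 14 days before period 1 and a washout of 7 to 28 days before period 2, so each patient who reaches period 2 should have a full pre-dose diary week in both periods. SAP 6.1.2 summarises baseline stool data, and SAP 6.1.3.3 models them for a different purpose, to check whether carryover differs between the sequences: "Baseline weekly stool frequency and the corresponding average stool form will be analyzed using the same method".

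Protocol 2.1 words the efficacy endpoint as "Changes from baseline in stool frequency and in stool form per Bristol Stool Chart". Neither document says which diary days form the baseline week. Protocol 3.1 names only the Day 1 pre-dose assessment as baseline, which cannot supply a weekly count.

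**The concern.** A crossover already removes a patient's stable level, because each patient is their own control. It does not remove fluctuation that lasts for one period, such as a change in diet or in disease activity that affects both the pre-dose week and the two treatment weeks that follow. If there is such fluctuation, the difference between a patient's two baselines predicts part of the difference between the two treatment periods. Without a baseline term that part stays in the error.

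With about 24 completers, a modest change in the standard error matters for the width of the 95% region around the frequency and form effects, which is the main efficacy output.

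**Working it through.** **Inputs from the documents.** 24 completers, 1:1 allocation (taken as 12 per sequence), two treatment weeks per period, washout 7 to 28 days, compound symmetry within each endpoint. The sample size section (protocol 11.6) is redacted and no standard deviation or correlation appears elsewhere, so there is no planned figure to reproduce. All correlations below are assumptions.

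**Set-up.** One endpoint, with weekly variance 1. Two weeks in the same period correlate rw, and two weeks in different periods correlate rb. The outcome is the two-week mean and the baseline is one week. Let D be the period 1 minus period 2 outcome and B the same difference in baseline.

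- Var(D) = 2[(rw - rb) + (1 - rw)/2]
- Var(B) = 2(1 - rb)
- Cov(D, B) = 2(rw - rb)
- R² = (rw - rb)² / {[(rw - rb) + (1 - rw)/2](1 - rb)}

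**True standard error.** Adjusted over unadjusted = sqrt[(1 - R²)(n - 3)/(n - 4)]. At n = 24 the factor is 21/20 = 1.05, the price of estimating the slope. For rb = 0.5, rw = 0.8: R² = 0.09/(0.4 × 0.5) = 0.45, and sqrt(0.55 × 1.05) = 0.76.

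**Standard error reported by the planned fit.** Compound symmetry over the four treatment weeks uses one pooled within-patient error. It combines 22 degrees of freedom between periods (expected mean square 1 + rw - 2rb) with 46 between weeks of the same period (expected mean square 1 - rw). Adjustment multiplies the first mean square by (1 - R²) and leaves it 21 degrees of freedom. For 0.5/0.8:

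- Unadjusted: (22 × 0.8 + 46 × 0.2)/68 = 0.394
- Adjusted: (21 × 0.44 + 46 × 0.2)/67 = 0.275
- Ratio: sqrt(1.05 × 0.275/0.394) = 0.856

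| rb / rw | R² | True SE ratio | Reported SE ratio |
|---|---|---|---|
| 0.5 / 0.5 | 0 | 1.025 | 1.02 |
| 0.5 / 0.6 | 0.067 | 0.990 | 1.01 |
| 0.7 / 0.8 | 0.167 | 0.935 | 0.98 |
| 0.5 / 0.7 | 0.229 | 0.900 | 0.96 |
| 0.6 / 0.8 | 0.333 | 0.837 | 0.92 |
| 0.5 / 0.8 | 0.450 | 0.760 | 0.86 |

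Simulation agreed. The true ratio ran from about 1.03 to 0.77 (0.763 in a separate run of 20,000 trials per scenario), and the reported ratio from 1.02 to 0.855.

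The reported column moves less because the pooled error is too small whenever rw exceeds rb. At 0.5/0.8 the unadjusted reported standard error is sqrt(0.394/0.8) = 0.70 of the true one. Adjustment raises this to about 0.78 in simulation (0.79 by formula), so reported and true values come closer together.

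**Residual drug effect in the period 2 baseline.** Suppose a fraction L of the effect remains in that baseline week for drug-first patients and is gone by the treatment weeks. The adjusted effect is then overstated by b × L/2, with b = (rw - rb)/(1 - rb). In the five scenarios with rw above rb, b runs from 0.2 to 0.6.

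- L = 10%: 0.2 × 0.10/2 = 1% to 0.6 × 0.10/2 = 3%
- L = 25%: 0.2 × 0.25/2 = 2.5% to 0.6 × 0.25/2 = 7.5%, so up to about 8%

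**The case against.** The strongest reply is that the plan's own covariance assumption leaves nothing to gain. If compound symmetry is extended to the baseline weeks, rw equals rb, R² is zero and adjustment costs about 5% in variance. That stands as the lower end of the range. But compound symmetry is a working assumption and not evidence. Weeks within a period are adjacent, while the two periods are separated by 7 to 28 days, so some excess within-period correlation is plausible.

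Second, after a 7-day washout the period 2 baseline week begins the day after the last period 1 dose. Keeping a possibly contaminated baseline out of the treatment estimate, and using it only to check carryover, is defensible. Gain and bias grow with the same slope, so the scenario with most to gain also has most to lose. This is why the unadjusted model should remain.

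Third, sequence, period and treatment is a standard crossover model, and the trial is declared non-confirmatory. Both are true and limit the weight of the point.

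A reader might infer more than the documents support:

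- **That the estimate is certainly less precise than it could be.** This depends on correlations the documents do not give.
- **That the omission biases the result, or that a chance baseline imbalance passes in full into the estimate.** Only the slope times the imbalance enters, and under randomisation this is chance variation, already counted in the standard error.
- **That adjustment makes missing-at-random more credible.** Nothing in the documents shows that dropout depends on baseline stool pattern. A two-period mean baseline would also be undefined for patients who leave before period 2, unless a rule is given.
- **That a plain change score is the remedy.** At 0.5/0.5 its variance is (0.5 + 1 - 0)/0.5 = 3 times the unadjusted one.

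**Conclusion.** The point holds as a possible loss of precision. The primary model leaves out baselines that are collected, already modelled and named in the endpoint, and gives no reason. For 24 completers and one endpoint at a time, adjustment would change the true standard error of the two-week contrast by about +2.5% when weeks within a period are no more alike than weeks across periods, and by about -23% at correlations of 0.5 between and 0.8 within periods. The standard error that the planned fit reports would change by about +2% to -14%. The joint region for frequency and form was not computed.

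The unadjusted estimate is not systematically biased by the omission. The case for change is that it is cheap and its downside is small and can be stated in advance, not that the planned analysis is invalid.

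**What to change.** In protocol 11.4.2 and SAP 6.1.3:

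1. Define the baseline week as the last 7 diary days before the first dose of each period.
2. Pre-specify a model that adds, for each endpoint, its own period-specific baseline and the patient's mean of the available baselines. The mean keeps within-patient and between-patient slopes separate. Using the available baselines keeps patients who leave before period 2. With these terms, modelling the weekly value or its change from baseline gives the same treatment estimate, which ties the analysis to the stated endpoint.
3. Report this model alongside the unadjusted model as now written, and read the adjusted result together with the carryover check in SAP 6.1.3.3.

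Fix this before results are used. The sponsor's trial team is unblinded throughout (protocol 6.5), so a baseline model added later could look data-driven.

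The cost is SAP wording and one more model run. The downsides to state are about one degree of freedom for the within-patient slope per endpoint (standard error up to 2.5% wider), and overstatement of the effect by about 1-3% if 10%, or up to about 8% if 25%, of it remains in the period 2 baseline of drug-first patients.

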1.2 Study purpose

The purpose of this study is to determine whether LJN452 improves the symptoms of bile acid diarrhea and to assess its safety and tolerability profile in patients with primary bile acid diarrhea (pBAD) to guide decision-making regarding further clinical development in this indication.

2 Study objectives

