3.2 Rationale of study design

This randomized, multi-center, double blind (patient and investigator blind, sponsor open label), placebo-controlled, cross-over study is designed to assess safety, tolerability and efficacy of LJN452 at 60 μ g relative to placebo in patients with pBAD, as assessed by a reduction in stool frequency and stool type score after 2 weeks of double-blind treatment.

A cross-over design reduces variability as the treatment comparison can be done within patient.

Randomization will be maintained at 1:1 ratio over the entire study in order to avoid any sequence bias.

Multiple sites will be used to enroll patient in this study due to the underlying prevalence of diagnosed pBAD. It is known that differences in criteria exist in the diagnosis of pBAD in different regions.

In order to maintain the scientific integrity of the study, investigators and patients will remain blinded regarding the allocation of active or placebo. The clinical trial team will be unblinded throughout the dosing phase to allow analysis of safety and PK/PD data.

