11.4.2 Statistical model, hypothesis, and method of analysis

A repeated measures analysis will be done for the two-dimensional endpoint: weekly stool frequency and the corresponding average stool form. The analysis will include fixed effects for sequence (Drug/Placebo or Placebo/Drug), Treatment (Week 1 Drug, Week 2 Drug, Week 1 Placebo or Week 2 Placebo), and period (1 or 2). The model will assume an arbitrary 2 by 2 covariance matrix for the two-dimensional endpoint (frequency, form) and a compound symmetry covariance matrix for each individual endpoint. Point estimates of the weekly & biweekly treatment effect on stool frequency and form will be reported together with 95% simultaneous confidence intervals (confidence ellipsoids).

Baseline weekly stool frequency and the corresponding average stool form will be analyzed similarly using the method described above to assess unequal carryover effects.

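### The visible plan gives the two primary stool measures only a joint confidence ellipsoid; adding a separate interval for each symptom would be tighter and would answer the stated question directly

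*SAP*

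**What the plan says.** Protocol 1.2 sets the aim: "The purpose of this study is to determine whether LJN452 improves the symptoms of bile acid diarrhea". Protocol 3.2 says that efficacy of the 60 µg dose against placebo is to be judged "as assessed by a reduction in stool frequency and stool type score after 2 weeks of double-blind treatment". Protocol 2.1 words the endpoint more neutrally: "Changes from baseline in stool frequency and in stool form per Bristol Stool Chart". SAP 6.1.1 lists both measures without ranking them: "The primary analysis variables are: a) stool frequency, b) and stool form assessed by the Bristol stool chart".

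Both documents fit one bivariate repeated measures model. Protocol 11.4.2 describes the output: "Point estimates of the weekly & biweekly treatment effect on stool frequency and form will be reported together with 95% simultaneous confidence intervals (confidence ellipsoids". SAP 6.1.3 says the same of its estimates, which "will be reported together with 95% simultaneous confidence intervals (confidence ellipsoids". Its heading mentions hypotheses, but the text states none and does not say how the ellipsoid is to be read.

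For each symptom separately, SAP 6.1.2 plans descriptive summaries, including the difference and percentage change between treatments, and SAP 6.1.3.2 plans boxplots. SAP 6.1.3.3 models a composite stool index. On status and size, SAP 1.4 says "This is a non-confirmatory trial" and "In this study approximately 30 patients will be enrolled to have 24 completers". The sample size and interim analysis sections are blacked out.

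**The concern.** The plan treats simultaneous confidence intervals and confidence ellipsoids as the same thing. They are not.

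- The ellipsoid is one region in the plane of (frequency effect, form effect). Its natural reference point is (0,0), and it departs from that point equally readily in every direction: both better, both worse, or one of each.
- A pair of simultaneous intervals says something about each symptom, with a direction.

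The question in protocol 1.2 and 3.2 is about improvement in named symptoms. If only the ellipsoid is shown, a reader who sees that it misses (0,0) learns that something moved, but not which symptom or which way with what certainty. If intervals are instead read off as the ellipsoid's projections, each is wider than it needs to be. Either way, the sponsor's development decision rests on a blurrier answer for each symptom than the same data and model could give.

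**Working it through.** **Inputs from the documents.** Two endpoints; 95% level; 24 completers of about 30 enrolled; two sequences in a 1:1 ratio.

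**Assumptions, because the documents give no figure.** Error degrees of freedom ν = n − 2 = 22 (two sequences); correlation ρ between the two estimated effects from 0 to 0.7; effect sizes as stated below. The plan's sample size cannot be re-derived because its basis is blacked out.

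**Step 1: interval width.** Each interval is estimate ± multiplier × SE.

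- Ellipsoid projection: √[2ν/(ν−1) × F(0.95; 2, ν−1)] = √[(44/21) × 3.467] = √7.264 = 2.695
- Bonferroni, 97.5% each: t(0.9875; 22) = 2.405
- Ordinary 95%: t(0.975; 22) = 2.074

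| Case | Projection | Bonferroni | Ordinary | Projection vs Bonferroni | Projection vs ordinary |
|---|---|---|---|---|---|
| n = 24, ν = 22 | 2.695 | 2.405 | 2.074 | 12% wider | 30% wider |
| n = 30, ν = 28 | 2.638 | 2.368 | 2.048 | 11% wider | 29% wider |
| Large df | 2.448 | 2.241 | 1.960 | 9% wider | 25% wider |

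If the mixed model used 44 or 66 df with multiplier √[2F(0.95; 2, df)], the projection would be 2.533 against 2.015, or 2.504 against 1.997. Both are about 25–26% wider than the ordinary interval, so the finding does not hinge on the choice of df. At ν = 22 a projected interval covers its own symptom 98.7% of the time, and the projected pair covers both effects about 97.5% of the time by simulation, against a nominal 95%.

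**Step 2: power for one symptom.** Assume frequency falls by 0.6 SD of the within-patient drug-minus-placebo difference. With 24 completers the effect is 0.6 × √24 = 2.94 SE. The noncentral t probability that the interval lies wholly below zero is:

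- projection (2.695): 60%
- Bonferroni (2.405): 70%
- ordinary 95% (2.074): 80%

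**Step 3: what exclusion of (0,0) means.** Simulation, 200,000 trials per scenario, ν = 22, effects in SE units (negative = reduction), ρ = 0 to 0.7:

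| True effect on one symptom, other symptom | Ellipsoid excludes (0,0) | Both ordinary 95% intervals below zero |
|---|---|---|
| 0, 0 | 5% | 0.1–0.8% |
| −3, 0 | 70–95% | 2.0–2.5% |
| −3, +1 (worse) | 75–99.5% | 0.1–0.2% |
| −3, −3 | 95–78% | 67–74% |
| +3, +3 (both worse) | 95–78% | 0% |

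The first row confirms that the region is correctly calibrated for (0,0). The rest show that missing (0,0) says little about which symptom moved. With positive correlation, the ellipsoid excludes (0,0) more readily for discordant effects than for concordant ones: at ρ = 0.7, 99.5% for −3/+1 against 78% for −3/−3.

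**The case against.** The best defence is that no test on the ellipsoid is planned. The trial is declared non-confirmatory, and nothing visible says that efficacy will be claimed if the region misses (0,0). The exclusion rates in Step 3 therefore describe a use that a reader might make of the ellipsoid, not a rule in the plan. This stands.

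A reader might also infer from protocol 3.2 that both symptoms must fall for success. The documents do not say so. That sentence is design rationale, and the objective and endpoint speak only of effect and change. This stands too.

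Direction is not hidden. Point estimates accompany the region, and SAP 6.1.2 gives treatment differences for each symptom, so the ellipsoid is not all that a reader has. But those summaries are descriptive, with no model-based interval, and the stool index mixes frequency, form and loperamide.

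The phrase may also mean that per-symptom intervals are intended. If they are projections, an unchanged symptom would fall wholly below zero only about (100 − 98.7)/2 = 0.65% of the time, so nothing is masked and the only cost is width. The ambiguity and the width cannot both bite in full under one reading. The text does not settle which applies, and that is part of the point.

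Finally, decision criteria may sit in the blacked-out sections, so their absence is not held against the plan.

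**Conclusion.** The point holds as a cheap and worthwhile improvement. The visible plan provides no explicit model-based interval for either primary symptom and equates a joint region with a pair of intervals. On the like-for-like comparison with Bonferroni, projected intervals are 9–12% wider, about 10 power points in the example (60% against 70%). The larger gap, 25–30% in width and about 20 points of power, is against an unadjusted interval. It is the relevant comparison only if no adjustment across the two symptoms is needed, for instance if both had to improve.

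Three stronger readings are not supported. The plan does not formally test a global null. It does not depart from a stated both-must-fall criterion. And there is no type I error failure: the ellipsoid has correct joint coverage, and its projections err on the safe side. The consequence is an imprecise or ambiguous reading of each symptom in a study meant to guide development.

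The width ratios depend little on df. The power and exclusion figures rest on the assumed effects, and the exclusion figures also on the assumed correlation.

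**What to change.** In SAP 6.1.3 and protocol 11.4.2, report from the same fitted model the drug-minus-placebo effect on stool frequency and, separately, on stool form, for Week 1, Week 2 and the two weeks combined. Give each effect:

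- an ordinary 95% interval; and
- a Bonferroni interval at 97.5% each, named as the 95% simultaneous interval. State that it is simultaneous over the two symptoms at a given time point.

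Keep the ellipsoid as a supporting figure, with a note that exclusion of (0,0) is not by itself evidence of improvement in either symptom. Whether both symptoms or either one must improve is for the sponsor to decide; the two sets of intervals serve both choices.

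The cost is a change of wording, one extra table and slightly more analysis work, with no new data or patients.
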